5.4. Scientific Rationale for Study Design

This study will be used to supplement the comprehensive chemistry, manufacturing control analytical plan for bridging the planned commercial drug product with the clinical trial drug product. Since the existing stores of clinical trial drug product have been exhausted, an indirect comparator/bridging study must be performed to demonstrate efficacy comparability.

This study design involves an open-label assessment of the planned commercial drug product compared to the marketed product (GlucaGen) within the T1DM population. The 2 study periods will be separated by a washout period of no less than 1 day (24 hours) and no more than 7 days due to the short half-life of NG (approximately $t_{1/2} = 25$ minutes). The second of the 2 study periods will expose the same patients to the alternate study arm (for example, those randomly assigned to receive NG LY900018 will receive IM GlucaGen for Period 2). This crossover design will allow each individual patient to act as an internal control.

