6.3.1. Meals and Dietary Restrictions

In both treatment periods, patients will fast for at least 8 hours prior to beginning the hypoglycemia induction procedure. Once this procedure is completed, the patients will receive a carbohydrate-rich meal. Patients will be given access to calorie-free water during the hypoglycemic procedure.

While resident in the CRU, patients may not consume any food or caloric drinks other than that provided by the CRU. When not resident in the CRU, patients will be encouraged to follow their normal diets. However, patients are encouraged to consume at least 100 g of carbohydrates during the washout period.

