6.3.3. Activity

Patients are encouraged to maintain their regular exercise habits for the duration of the study. However, patients should avoid strenuous exercise 48 hours prior to study days.

During the procedure to induce hypoglycemia, patients should remain recumbent or sitting in the CRU until the end of the procedure.

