10.1. Sample Size Determination

Assuming a 5% dropout rate, the study will enroll approximately 70 patients to have 66 patients completing both treatment visits with evaluable primary outcome.

A total of 66 patients are required in the study in order to achieve the primary objective with at least 90% power under the following assumptions:

- A treatment success rate of 98% for both treatments
- A noninferiority margin of 10%
- One-sided alpha level of 0.025
- A within-patient correlation of zero between 2 treatment visits

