10.3.1. Efficacy Analyses

10.3.1.1. Primary Efficacy

The primary outcome is the treatment success, which is defined as an increase in PG to ≥ 70 mg/dL or an increase of ≥ 20 mg/dL from PG nadir within 30 minutes after receiving glucagon, without receiving additional actions to increase the PG concentration. The nadir is defined as the minimum PG concentration at the time of or within 10 minutes following glucagon administration.

The primary analysis will be a treatment group comparison of the primary outcome. The percentage of treatment successes in each treatment and the difference in percentages will be computed. A 2-sided 95% CI will be obtained from the 1-sample mean of the paired differences in primary outcome (1=outcome observed; 0=outcome not observed) across 2 treatment visits. Noninferiority of NG will be declared if the upper limit of a 2-sided 95% CI constructed on the difference in percentages (IMG – NG) is less than the noninferiority margin of 10%.

The proposed noninferiority margin of 10% has been chosen based on the previously completed Phase 3 study (Rickels et al. 2016).

Primary efficacy analysis will only include patients who complete both treatment visits with evaluable primary outcome. The following will be considered as nonevaluable primary efficacy outcome and excluded from the analysis related to primary efficacy outcome:

- Patients with at least 1 treatment visit in which the lowest PG concentration at the time of or within 10 minutes following glucagon administration is ≥ 70 mg/dL;
- Patients receive an external measure to raise PG concentration either before glucagon administration or within the first 10 minutes of glucagon administration.

Plasma glucose concentrations assessed through a central laboratory will be used to assess treatment success. If a central laboratory measurement is missing, the SuperGL (or equivalent)

measurement from that time point will be used in general with the following additional provisions:

- Out-of-window blood draws (blood draws taken before/after the midpoint between consecutive planned measurements) that occur prior to the 30-minute time point will be included.
- Central laboratory PG concentrations and SuperGL (or equivalent) concentrations at the 30-minute time point that are measured more than 35 minutes after administration of glucagon will be considered missing.

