10.3.3.2. Pharmacokinetic Statistical Inference

Log-transformed PK parameters (such as C_{max} and AUC parameters) will be evaluated in a linear mixed-effects model with fixed effects for treatment, period, and sequence, and a random effect for patient. The treatment differences will be back-transformed to present the ratios of geometric means and the corresponding 90% CI.

The T_{max} will be analyzed using the Wilcoxon signed rank test. Estimates of the median difference based on the observed medians, 90% CIs, and p-values from the Wilcoxon test will be calculated.

Exploratory analyses may be performed for other PK parameters as deemed appropriate.

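### The primary noninferiority estimate ignores period and sequence, so any common period effect enters it in proportion to sequence imbalance; the likely effect is small and the fix nearly free

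*Protocol*

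**What the plan says.** **Primary analysis.** Protocol Section 10.3.1.1 states: "A 2-sided 95% CI will be obtained from the 1-sample mean of the paired differences in primary outcome". NG is noninferior if the upper limit for IMG − NG is below 10 points. There is no period or sequence term. The set is restricted to patients evaluable at both visits.

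**Other analyses.** Section 10.3.3.2 models log-transformed pharmacokinetic parameters with "fixed effects for treatment, period, and sequence, and a random effect for patient". Section 10.3.4.2 uses the same terms for the plasma glucose parameters.

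**Design.** The two inductions are 1 to 7 days apart (Section 5.1). Section 5.4 gives only a drug-elimination reason for that interval: "no more than 7 days due to the short half-life of NG".

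**Balance.** Section 7.2 refers to a randomization schedule without giving a ratio. Section 5.2 replaces patients who drop out or are not evaluable, and the replacement takes the same sequence. Sections 5.2 and 10.1 plan about 70 enrolled to obtain at least 66 evaluable pairs.

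**The concern.** A mean over all pairs equals the treatment difference only if there is no period effect or the analysed sequences are equal in size. The washout rationale covers drug carryover. It does not address whether the glucose response is the same at a second induced hypoglycemia, possibly 24 hours after the first. One instruction also differs between periods: Section 6.3.1 says "patients are encouraged to consume at least 100 g of carbohydrates during the washout period", and that interval exists only before Period 2.

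If success is less frequent in Period 2 and one sequence is larger, part of the decline is counted as a treatment difference, for or against NG depending on which sequence is larger. One net failure among 66 pairs is 1/66 = 1.5 points, so small shifts can matter near the boundary.

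**Working it through.** **1. The plan's own figure.** Inputs from Section 10.1: 98% success on both treatments, margin 10 points, one-sided 0.025, zero within-patient correlation, 66 pairs.
- Variance of a paired difference: 2 × 0.98 × 0.02 = 0.0392.
- Standard error: √(0.0392/66) = 0.0244.
- Wald power: Φ(0.10/0.0244 − 1.96) = 98.4%. Exact power of the planned paired-t interval is 96.3%.
- Enrolment: 66/0.95 = 69.5, so 70.

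The stated power of at least 90% holds, and nothing below changes N.

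**2. Bias formula.** Let τ be the true IMG − NG difference in success, δ the Period 2 minus Period 1 failure rate (common to both treatments), and n1 and n2 the evaluable NG-first and IMG-first patients.
- NG-first patients receive IMG in Period 2, so their expected difference is τ − δ.
- IMG-first patients receive NG in Period 2, so theirs is τ + δ.
- The planned mean therefore has expectation τ − δ(n1 − n2)/N.
- The unweighted average of the two sequence means has expectation τ at any split.

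**3. Size of the shift.** The value of δ is assumed; the documents give none.

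| Split (N = 66) | δ = 2 points | δ = 5 points | δ = 10 points |
|---|---|---|---|
| 33:33 | 0 | 0 | 0 |
| 34:32 | 0.06 | 0.15 | 0.30 |
| 35:31 | 0.12 | 0.30 | 0.61 |
| 36:30 | 0.18 | 0.45 | 0.91 |

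Example: 5 × (36 − 30)/66 = 0.45.

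**4. How unequal the sequences could be.** If 70 are enrolled 35:35 and the four spare patients are all lost from one sequence, the split is 31:35 with 66 pairs still available. On one reading of Section 5.2, no replacement is then triggered. Equal allocation is itself an assumption.

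**5. What the document suggests about δ.** Section 3.2 reports 74 of 75 successes on NG and 75 of 75 on IMG in the predecessor study, that is, one failure in 150 treatments. If these were 75 patients treated in both periods, the observed period difference was at most 1/75 = 1.3 points. The shift would then be 1.3 × 6/66 = 0.12 points at 36:30 and 1.3 × 2/66 = 0.04 at 34:32.

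**6. Operating characteristics.** Simulation of 200,000 trials per scenario, with independent outcomes and 2% IMG failure in Period 1. The planned mean is compared with the sequence average.

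| NG-first:IMG-first, δ | Power at τ = 0 | False noninferiority at τ = 10 points |
|---|---|---|
| 33:33, 0 | 96.3% vs 96.3% | 4.8% vs 4.8% |
| 33:33, 5 | 78.2% vs 78.2% | 3.5% vs 3.5% |
| 35:31, 5 | 80.5% vs 80.2% | 3.9% vs 3.8% |
| 31:35, 5 | 75.8% vs 77.7% | 3.1% vs 3.4% |
| 36:30, 5 | 81.6% vs 77.4% | 4.2% vs 3.3% |

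At τ = 0 the two methods reach different conclusions in at most 0.2% of trials at 34:32, even with a 10-point decline. The figure is 1.8% at 31:35 with a 5-point decline, and 4 to 5% at 36:30 or 28:38 with a 5-point decline.

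**The case against.** - **The replacement rule targets this imbalance.** This stands in large part. Section 5.2 covers both dropouts and nonevaluable completers and keeps the sequence. It does not assure balance: enrolment already allows for losses, replacement aims at a total of 66, and no allocation ratio is given.
- **Period effects of 5 to 10 points are far above anything in the document.** This stands. The predecessor result points to about 1 point, though only indirectly, because its washout is not stated.
- **The dietary and exercise rules standardise the visits.** This mostly stands. The 48-hour exercise instruction, "patients should avoid strenuous exercise 48 hours prior to study days", applies before every study day, and fasting applies in both periods. Neither is evidence of a period effect. The carbohydrate advice is specific to the washout, but it is only encouragement.
- **A simple paired difference is legitimate for a binary endpoint with rare failures, and Section 10.3.1.1 leaves additional analyses to the SAP.** The first part is fair: the modelled parameters are continuous, so the difference in approach is not a contradiction. But the protocol itself fixes the estimator that decides noninferiority.

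A reader might infer that a Period 2 decline passes directly into the treatment difference. It does not: only the fraction (n1 − n2)/N enters, which is 3% of the decline at 34:32 and 9% at 36:30. A reader might also infer that the omission inflates the type I error. At the splits tabulated, the error rates with a period effect do not exceed the 4.8 to 4.9% that the planned interval already has with no period effect.

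**Conclusion.** The point holds as a minor weakness of specification. The confirmatory estimate does not analyse by the randomised sequences and is open to an additive period bias that the study's other models remove. The shift is 0.15 to 0.45 points for an assumed 5-point decline at splits from 34:32 to 36:30, nil at balance, and near zero if failures are as rare as in the predecessor study. Larger declines or splits such as 38:28 are assumptions that the documents do not support.

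Three things fall outside the point. Power lost to a Period 2 decline is mostly due to lower success rates: at 33:33 a 5-point decline takes power from 96.3% to 78.2% with either method. Carryover that differs between sequences is not removed by a period adjustment. The small-sample type I error of about 4.9% for the paired interval is a separate matter.

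**What to change.** In Section 10.3.1.1, define the estimate of IMG − NG as the unweighted average of the two sequence-specific mean paired differences. Pool the variance within sequence and use N − 2 degrees of freedom. Keep the unadjusted mean as a supportive analysis. Make the choice before data are seen, since choosing between the two afterwards would be open to challenge.

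**Cost.** One sentence and a few lines of code. At equal sequence sizes the point estimate is identical to the planned one. The adjustment uses one degree of freedom and gives a slightly wider interval when the sequences are unequal and there is no period effect: about 0.2 points of power at 36:30 (96.3% to 96.1%) and about 1 point at 38:28. The planned 66 pairs do not change.

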Bedside glucose safety measurements (SuperGL laboratory analyzer)		X		Samples will be collected throughout the study procedure. During the hypoglycemia induction procedure, plasma glucose concentration will be measured no more than 10 minutes apart while the plasma glucose concentration is ≥ 100 mg/dL and no more than 5 minutes apart when the plasma glucose concentration is < 100 mg/dL. Post-glucagon administration, plasma glucose concentration will be measured every 5 minutes for the first 30 minutes and every 10 minutes up to 90 minutes.
Sample collection for measurement of plasma glucose		X		Samples will be collected pre-dose (i.e., immediately prior to glucagon administration) and at 5, 10, 15, 20, 25, 30, 40, 50, 60, and 90 minutes post-glucagon administration. Samples to be processed at a central laboratory.
Exploratory sample		X (Period 1 only)	X	Serum samples will be collected prior to the procedure to induce hypoglycemia.

Genetic sample		X (Period 1 only)		
----------------	--	-------------------------	--	--

Abbreviations: CRU = clinical research unit; DPC = dodecylphosphocholine; ECG = electrocardiogram; ED = early discontinuation; HbA1c = hemoglobin A1c; IM = intra-muscular; NG = nasal glucagon; PG = plasma glucose.

Note: if multiple procedures take place at the same time point, the following order of the procedure should be used: ECG, vital signs and venipuncture.

3. Introduction

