9.2.3. Procedures for Insufficient Response to Glucagon Administration

If the PG is declining too fast or symptoms become consistent for the progression to severe hypoglycemia to occur, the investigator may decide to start a glucose infusion to prevent a deterioration of the situation. Continuous venous access will be used while the patient resides in the CRU to enable immediate delivery of IV glucose if needed. If, following the administration of glucagon, a patient's PG concentration remains <55 mg/dL at 30 minutes or <60 mg/dL at 45 minutes, IV glucose may be given as appropriate to the clinical situation. If IV glucose is given or additional glucagon is given, any remaining blood samples for the admission will still be collected.

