- If a PG concentration is missing for both central laboratory and SuperGL (or equivalent) measurements, the missing value will be imputed using linear interpolation of central laboratory values.

Additional analysis will be performed if deemed necessary. The details will be provided in the SAP.

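### Could IV glucose given just after 30 minutes turn a failed visit into an imputed primary-endpoint success?

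*Protocol*

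**What the plan says.** Protocol Section 10.3.1.1 defines success as reaching PG of at least 70 mg/dL, or rising at least 20 mg/dL from nadir, "within 30 minutes after receiving glucagon, without receiving additional actions to increase the PG concentration". Central laboratory values are used first. If one is missing, the SuperGL bedside value from that time point replaces it. A 30-minute value from either source "measured more than 35 minutes after administration of glucagon will be considered missing". If both are missing, "the missing value will be imputed using linear interpolation of central laboratory values".

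The same section lists what makes a patient nonevaluable. On rescue the entry reads: "Patients receive an external measure to raise PG concentration either before glucagon administration or within the first 10 minutes of glucagon administration". Rescue later than that is not on the list.

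The Schedule of Activities (Section 2) sets central PG draws before dosing and "at 5, 10, 15, 20, 25, 30, 40, 50, 60, and 90 minutes post-glucagon administration". For the bedside analyser it says: "Post-glucagon administration, plasma glucose concentration will be measured every 5 minutes for the first 30 minutes and every 10 minutes up to 90 minutes".

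Section 9.2.3 permits IV glucose if PG stays below 55 mg/dL at 30 minutes or below 60 mg/dL at 45 minutes. It also permits it earlier if PG is falling too fast or "symptoms become consistent for the progression to severe hypoglycemia to occur, the investigator may decide to start a glucose infusion". Sampling then goes on: "If IV glucose is given or additional glucagon is given, any remaining blood samples for the admission will still be collected".

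Section 10.3.1.2.1, on the secondary PG summaries, drops measurements taken after an intervention to raise PG.

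**The concern.** The imputation rule for the primary endpoint names no ineligible neighbours. A missing 30-minute value lies between the central draws at 25 and 40 minutes, and sampling continues after rescue. If IV glucose starts between about 30 and 40 minutes, the 40-minute value reflects that glucose, yet as worded it may still feed the interpolation.

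The nonevaluable list does not reach this case, because it stops 10 minutes after glucagon. The success definition does mention additional actions, but it gives that condition no time window of its own. If the condition is read as covering only the 30 minutes after dosing, an infusion begun at 32 minutes would not cancel an imputed success. Meanwhile the secondary PG analysis excludes that same 40-minute sample.

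If the route were real, a response to IV glucose would be counted as a response to glucagon. In a trial that expects about 2% failures, the noninferiority verdict can rest on a single patient.

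**Working it through.** **1. The interpolation.** The draw times (Section 2) are 25, 30 and 40 minutes. Linear interpolation gives

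PG30 = PG25 + (30 − 25)/(40 − 25) × (PG40 − PG25) = 2/3 × PG25 + 1/3 × PG40.

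The success threshold is T = min(70, nadir + 20), so the smallest PG40 that yields an imputed success is 3T − 2 × PG25. The glucose values below are illustrations; the protocol gives no post-rescue PG.

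| Nadir | T | PG25 | PG40 needed | PG40 assumed | Imputed PG30 | Scored |
|---|---|---|---|---|---|---|
| 45 | 65 | 52 | 195 − 104 = 91 | 115 (after IV glucose) | (104 + 115)/3 = 73.0 | success |
| 45 | 65 | 58 | 195 − 116 = 79 | 100 (after IV glucose) | (116 + 100)/3 = 72.0 | success |
| 45 | 65 | 58 | 79 | 65 (no glucose) | (116 + 65)/3 = 60.3 | failure |

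The mechanism is arithmetically possible.

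**2. What one patient is worth.** Section 10.3.1.1 uses a 95% interval for the mean paired difference (IM − nasal). Take n = 66, b nasal-only failures and no IM-only failures. The mean is b/66, the variance is (b − b²/66)/65, and t(0.975, 65) = 1.997.

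- b = 3: mean 4.55%, SD 0.2099, SE 0.2099/√66 = 2.58%. Upper limit 4.55 + 1.997 × 2.58 = 9.71%, below 10%.
- b = 4: mean 6.06%, SD 0.2404, SE 2.96%. Upper limit 11.97%, above 10%.

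One rescored patient can decide the verdict, but only if there are about four nasal-only failures to begin with.

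**3. A ceiling on how often this could matter.** The protocol gives no rate of missing 30-minute values. Assume that a fraction m of failing visits has no usable 30-minute value from either source, and that every such visit is rescued and imputed as a success. I enumerated all discordant-pair outcomes exactly, with n = 66 and within-patient correlation zero (Section 10.1), and computed the probability of failing before rescoring and passing after it.

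| True success, IM v nasal | m = 1% | m = 5% |
|---|---|---|
| 98% v 98% (Section 10.1) | 0.11% | 0.54% |
| 98% v 96% (96% assumed) | 0.54% | 2.6% |

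The true deficit is 0 points in the first row and 2 points in the second, both well inside the 10% margin. A pass is the correct conclusion in each, so these figures measure the chance that the verdict changes.

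**4. What must coincide.** All of the following are needed in one visit:

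- No value up to 30 minutes meets the criterion. Out-of-window draws before 30 minutes are kept and count.
- Neither a central nor a bedside 30-minute value exists, or each was drawn after 35 minutes, although bedside readings are due every 5 minutes and Section 9.2.1 requires an investigator or designee at the bedside for 90 minutes.
- Rescue starts before the 40-minute draw. Rescue under the below-55-at-30-minutes rule presupposes a 30-minute reading, and an on-time bedside reading replaces the missing central value, so nothing is imputed. The first example in step 1 would normally be stopped here. What remains is mainly symptom-driven rescue.
- The 40-minute value is high enough.
- The analyst reads the additional-actions condition as ending at 30 minutes.

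**5. Prior experience in the document.** Section 3.2 reports that adults in the two completed inpatient studies recovered without additional actions to raise glucose. In the study on which this design is modelled, 74 of 75 nasal-treated patients succeeded by 30 minutes. The one who did not met both criteria at 40 minutes.

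**The case for a change.** The best case for a change is that the protocol chose to fix the source hierarchy, the time windows and the imputation rule itself, so a poorly bounded rule is a defect of this text and not a detail left to the SAP. The two readings of the additional-actions condition are both grammatically available, and two analysts could score the same rescued patient differently. The protocol provides for both sources being missing, so it foresees the situation. The trial is open-label, which makes it better to settle scoring before data are seen. One sentence would do it.

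Part of this stands: the text contains no explicit bar, and the condition has no stated window. The claimed inconsistency with Section 10.3.1.2.1 is weaker than it looks. That section summarises raw glucose values, where nothing else deals with rescue, so it needs its own exclusion. The primary endpoint deals with rescue inside the definition of success. Reading the condition so that a rise due to IV glucose counts as success would defeat its evident purpose, and an analyst is unlikely to adopt that reading.

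The simple remedy also has a flaw. A blanket rule scoring every rescued visit without prior success and without a usable 30-minute value as a non-success would collide with the nonevaluable rule for rescue before glucagon or in the first 10 minutes after it. It would need a carve-out, and it would still have to state the time window of the condition.

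**Conclusion.** No change to the plan is called for. Section 10.3.1.1 leaves unsaid that values taken after rescue may not be used for interpolation, but the success definition already implies the answer, and analysts applying it sensibly would score such a visit as a failure. The remaining route depends on an unnatural reading together with several uncommon events in one visit.

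The ceilings of 0.11% to 0.54% (98% in both arms) and 0.54% to 2.6% (nasal 96%) rest on assumed rates of 1% to 5%, zero correlation, and every affected visit being both rescued and imputed as a success. The true figure is lower, and none of these is a false noninferiority rate. If the sponsor revises the section for another reason, a sentence making the exclusion and the window of the condition explicit, with visits already nonevaluable set apart, would do no harm. The expected gain is negligible.
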